#### 5.4.2 Quality of Life (QoL)

QoL data from the EORTC QLQ-C30 and QLQ-LC13 questionnaire are collected for all enrolled patients at Screening, every imaging/tumor assessment visit, and the Safety Follow-up Visit.

QoL analyses will be based on the **As-Treated Population**. The global health status/QoL, functional scales, symptom scales, and lung cancer related symptoms will be summarized for each evaluation time point using descriptive statistics. Additional analyses although not pre-specified may be conducted for certain items of interest.

### 5.5 Secondary Analysis

#### 5.5.1 Evaluable Population

Modified ORR as described in [Section 5.1](#), unconfirmed ORR, DCR, and PFS will be analyzed for the **Evaluable Population**.

#### 5.5.2 Sensitivity Analyses

Analyses of the primary and secondary outcomes will be performed only for patients who are positive for exon 20 mutations based on the central tissue testing.

### 5.5.3 Subgroup Analysis

Analyses of the primary and secondary endpoints will be performed for the following subgroups.

- a) Per FDA Type C meeting minutes of July 13, 2018, subgroup analysis will be conducted for individual mutation and various clusters of mutations within exon 20 in order to evaluate prognostic implications, which may include
  - individual mutation type with higher counts of patients
  - other meaningful mutation clusters
- b) Patient subgroups based on prior therapy for locally advanced or metastatic NSCLC, such as
  - patients who had prior platinum-based chemotherapy
  - patients who had 2 lines of prior treatment, including platinum-based chemotherapy with or without immunotherapy, other tyrosine kinase inhibitor (TKI) or other systemic therapy, for locally advanced or metastatic NSCLC
  - patients who had 3 lines of prior treatment, including platinum-based chemotherapy with or without immunotherapy, other tyrosine kinase inhibitor (TKI) or other systemic therapy, for locally advanced or metastatic NSCLC

### 5.5.4 Tumor Assessment by Local Review

ORR, DCR, DoR, and PFS based on tumor assessment by local imaging review will be reported separately using statistics described above for the **As-Treated Population** and the **Evaluable Population**. Best overall response and modified best overall response will be determined based on tumor measurement using RECIST v1.1 following [Section 5.1](#). The agreement of best overall response between central and local imaging review will be displayed using cross table and evaluated using weighted kappa.

### 5.5.5 Exploratory Analysis

The effect of treatment exposure on tumor response (PR, SD, and PD only) will be evaluated using a logistic regression model. For this exploratory analysis, it is assumed the tumor response of a subject at a time point depends on average daily dose between last and current tumor assessment time points. The average daily dose from last tumor assessment to current tumor assessment will be calculated as total dose in the period divided by total days in the period. The distribution of average dose for different tumor response (PR, SD, PD) will also be summarized using descriptive statistics.

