### 2.1 Study Design and Treatment Plan

This is a Phase 2, open-label, single-arm, multicenter study to evaluate the efficacy and the safety/tolerability of poziotinib in various cohorts. Cohorts 1-4 of the study will enroll up to 174 NSCLC patients previously treated with any systemic therapy (87 patients with EGFR exon 20 insertion mutations and 87 patients with HER2 exon 20 insertion mutations) and up to 140 treatment-naïve NSCLC patients (70 patients with EGFR exon 20 insertion mutations and 70 patients with HER2 exon 20 insertion mutations).

The **Screening** period (**Day -30 to Day -1**) lasts up to approximately 30 days prior to **Cycle 1, Day 1**. Patients must meet all Inclusion/Exclusion Criteria to participate in the study. Eligible patients will provide written Informed Consent prior to undergoing any study procedures.

Each treatment cycle is 28 calendar days in duration. There will be four patient cohorts and eligible patients will be enrolled into each cohort in parallel based on EGFR or HER2 exon 20 mutant status and prior treatment status:

- **Cohort 1:** Previously treated patients with EGFR exon 20 insertion mutation positive metastatic NSCLC
- **Cohort 2:** Previously treated patients with HER2 exon 20 insertion mutation positive metastatic NSCLC
- **Cohort 3:** Treatment naïve patients with EGFR exon 20 insertion mutation positive metastatic NSCLC
- **Cohort 4:** Treatment naïve patients with HER2 exon 20 insertion mutation positive metastatic NSCLC

Toxicity will be assessed based on the grade of the adverse events (AEs) using CTCAE version 4.03.

Poziotinib will be taken orally, once daily (QD) with food and a glass of water at approximately the same time each morning. On **Day 1** of each 28-day cycle, the patient's absolute neutrophil count (ANC) must be  $\geq 1.5 \times 10^9/L$  and platelet count must be  $\geq 100 \times 10^9/L$  before administering poziotinib.

All patients will be treated until 24 months of treatment, disease progression, death, intolerable AEs, or other protocol-specified reason for patient withdrawal.

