## 2.3 Tumor Assessments

This section provides general description of tumor assessments. All images acquired at baseline and follow-up will be sent to Bioclinica, Inc. for central radiographic review by an Independent Review Committee (IRC) for response evaluation based on RECIST criteria, Version 1.1 [2]. Details are found in Bioclinica Independent Review Charter for SPI-POZ-202, including a list of all pre-specified modifications from RECIST 1.1 criteria.

Patient eligibility for enrollment will be based on the scans performed before the patient signed the ICF and review by the Site Principal Investigator. After patient enrolled into the study, baseline tumor assessment is required. All baseline and follow-up tumor assessments must be performed using computed tomography (CT), positron emission tomography (PET)/CT, or magnetic resonance imaging (MRI). The baseline tumor assessment must be performed within 2 weeks prior to, or on **Cycle 1, Day 1**. In situation that images are incomplete at baseline evaluation (i.e. missing images from some body sites), the most recently available images of the missing body sites prior to baseline (ie. at Screening) may be sent to Bioclinica as part of baseline evaluation.

For patients with known brain metastases, a baseline brain MRI scan will also be performed to assess the status of brain metastases if present.

Tumor assessments will be performed at

- approximately 4 weeks (**Cycle 2, Day 1**) [ $\pm 7$  days], 8 weeks of treatment (**Cycle 3, Day 1** [ $\pm 14$  days]), and approximately every 8 weeks ( $\pm 14$  days) thereafter [Original Protocol]
- approximately 4 weeks (**Cycle 2, Day 1** [up to **Cycle 2, Day 7**]), 8 weeks (**Cycle 3, Day 1** [up to **Cycle 3, Day 7**, with at least 28 days from previous tumor assessment]), and approximately every 8 weeks ( $\pm 7$  days) thereafter [Amendment 1 & 2]

For each patient, subsequent tumor assessment must use the same radiographic technique performed at baseline, either CT, PET/CT, or MRI. Tumor assessments will be made according to RECIST criteria, Version 1.1 [2] using appropriate radiographic imaging or other techniques. Patient enrollment and clinical decisions will be based on local imaging review and the efficacy assessments for final analysis will be based on the central imaging review by IRC at Bioclinica.

Measurable and non-measurable lesions that will not be followed by radiographic methods should be documented appropriately.

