## 5.2 Primary Endpoint

### 5.2.1 Objective Response Rate (ORR)

The primary endpoint is ORR and is defined as the proportion of patients whose best overall response is confirmed to be CR or PR from the first dose of poziotinib until the last tumor assessment on study. The unconfirmed ORR, which does not require confirmation scans for CR/PR, will also be provided.

ORR and unconfirmed ORR will be estimated with count, percentage and 95% CI (Clopper-Pearson).

The test of hypothesis of the primary endpoint will be performed using the 95% CI. The prespecified primary endpoint criteria for each cohort is stated in [Section 3.2](#).

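### The exposure-response logistic model in SAP Section 5.5.5 uses repeated time-point records with no handling of within-patient correlation and no time term, and it drops CR time points

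*SAP*

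**What the plan says.** SAP Section 5.5.5 names the method in one sentence: "The effect of treatment exposure on tumor response (PR, SD, and PD only) will be evaluated using a logistic regression model". It then sets the unit and the exposure: "it is assumed the tumor response of a subject at a time point depends on average daily dose between last and current tumor assessment". The exposure is the total dose in each interval between assessments divided by the days in it, so it can change from record to record within a patient. The accompanying dose summary has the same restriction: "The distribution of average dose for different tumor response (PR, SD, PD) will also be summarized using descriptive statistics".

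The section does not say whether the model is binary, cumulative or multinomial. It names no random effect, GEE or robust variance, and no term for time or assessment number. It gives no reason for leaving out CR.

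Three other places bear on this:
- Section 2.3 schedules scans at about 4 and 8 weeks "and approximately every 8 weeks" thereafter.
- Section 2.1 says "All patients will be treated until 24 months of treatment, disease progression, death, intolerable AEs, or other protocol-specified reason for patient withdrawal".
- Section 5.2.1 defines ORR as the "proportion of patients whose best overall response is confirmed to be CR or PR", and Table 1 lists CR as a possible time point response.

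**The concern.** Three features of the specification affect what the dose coefficient would mean.

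**Repeated records.** Records from one patient are correlated. Under Section 2.3.2 PR is judged against the baseline sum of diameters, so once reached it tends to carry over from scan to scan. An ordinary logistic regression, which is the literal reading of the text, counts every record as new information.

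**Time.** Progressing patients stop treatment, so late records come mostly from patients who respond or stay stable. If dose reductions accumulate over the same period, late records combine lower dose with more PR. Without a time term the model can attribute this to dose.

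**CR time points.** A question about dose and response is put to data from which the best response category has been removed.

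At stake is a misleading p-value or interval, and possibly a misleading sign, for the association between dose and response.

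**Working it through.** The SAP gives no standard error, power or error rate for this model, so there is no stated figure to reproduce. What follows shows the size of the problem under stated assumptions.

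**1. Records per patient.** There is one scan at week 4, then scans from week 8 to week 104 (24 months) every 8 weeks: (104 − 8)/8 + 1 = 13. The maximum is 1 + 13 = 14. Most patients will have fewer.

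**2. Approximate variance inflation.** For m records per patient, within-patient dose correlation ρx and within-patient response correlation ρy, the design effect is 1 + (m − 1)·ρx·ρy. The true SE is the ordinary SE multiplied by its square root. Neither correlation is in the SAP, so a range is shown:
- m = 3, ρx = 0.5, ρy = 0.5: 1 + 2 × 0.25 = 1.50; factor 1.22.
- m = 6, ρx = 0.8, ρy = 0.5: 1 + 5 × 0.40 = 3.00; factor 1.73.
- Any m, ρx = 0: 1.00; factor 1.00.
- m = 6, ρx = −0.1, ρy = 0.5: 1 − 5 × 0.05 = 0.75; factor 0.87.

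**3. Simulation with no dose effect and no time trend.** Settings: 87 patients (the size of Cohorts 1 and 2), a binary response, a patient random intercept with SD 2.5 on the logit scale, 600 replicates, and a two-sided 5% test (the general rule in Section 3.3.1).

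| Records per patient | Dose correlation | True SE / ordinary SE | Rejections, ordinary | Rejections, clustered |
|---|---|---|---|---|
| 3 | within patient only | 0.72 | 1.0% | 5.8% |
| 3 | 0 | 1.01 | 4.7% | 5.0% |
| 3 | 0.5 | 1.17 | 9.3% | 3.8% |
| 3 | 0.8 | 1.38 | 14.7% | 5.0% |
| 5 | within patient only | 0.74 | 0.3% | 6.3% |
| 5 | 0 | 1.00 | 5.0% | 5.7% |
| 5 | 0.5 | 1.40 | 16.0% | 5.0% |
| 5 | 0.8 | 1.51 | 17.8% | 5.0% |
| 8 | within patient only | 0.73 | 0.5% | 4.8% |
| 8 | 0 | 1.00 | 4.8% | 5.5% |
| 8 | 0.5 | 1.67 | 25.0% | 5.8% |
| 8 | 0.8 | 1.91 | 27.2% | 5.5% |

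The direction of the error follows the dose correlation. Patient-clustered standard errors hold the test near 5% in every row.

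**4. Simulation with no dose effect but with drop-out at PD.** PR persists once reached, and dose steps down over time independently of response. There are 87 patients. Two sets of assumptions were used:
- **Set A:** 30% responders with a lower risk of progression; a 2 mg step-down with probability 0.15 to 0.45 per interval; about 4.4 scans per patient; PR against SD or PD; 400 trials per setting.
- **Set B:** the same mechanism, with about 3.8 scans per patient.

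| Model | False rejections, set A | False rejections, set B |
|---|---|---|
| Ordinary logistic, dose only | 61-81% | 44-90% |
| Clustered by patient, dose only | 32-58% | 19-75% |
| Clustered by patient, plus assessment number | 7-8% | 4-9% |

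With dose only, the mean slope was negative in both sets (about −0.15 log-odds per mg in set A): lower dose appeared to go with PR. With assessment number added, the mean slope in set A was about 0. Clustering alone therefore does not cure this part.

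**5. CR.** Section 5.2.1 counts CR as response and Table 1 allows it at a time point, while Section 5.5.5 excludes it from both the model and the dose summary. No arithmetic is possible, because the SAP gives no expected number of CRs.

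**The case against.** The strongest reply is that the SAP never says the records are independent. GEE and random-intercept models are also logistic regressions, so the gap may be one of specification rather than a wrong method. This is fair as far as it goes, but an analyst following the text alone would fit the ordinary model, and no time term is named under any reading.

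A reader might infer that the standard errors must be too small. The documents do not support that. They give no dose or response correlations, the exposure is specific to each interval, and the table shows no error at correlation 0 and a reversed one when dose varies only within patient. Persistence is plausible, since Section 6.1 treats reductions as steps to 14, 12, 10 and 8 mg and sets temporary fluctuation apart, but it remains an assumption.

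A reader might also infer that the best responders are excluded. They are not. CR time points are dropped, but a patient who reaches CR can still contribute PR or SD records. Under Table 1, a target-lesion CR with persisting or unevaluable non-target disease is a PR and stays in. If CRs are few, the effect is small.

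It can be said, too, that the SAP gives neither the timing nor the frequency of dose reductions, so a reversed sign is not established. That stands: the simulation shows it can happen, not that it will.

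Finally, the analysis is labelled exploratory and carries no decision rule. This limits the consequence but does not make the estimate reliable.

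**Conclusion.** The point holds as a defect in how Section 5.5.5 specifies the model. Repeated time-point records are analysed with no method for within-patient correlation and no time term, and CR time points are excluded without a reason.

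The size depends on assumptions the SAP does not supply. For a persistent dose (correlation 0.5 to 0.8) and 3 to 8 records per patient, ordinary standard errors are too small by a factor of 1.17 to 1.91, and the nominal 5% test rejects about 9-27% of the time. If reductions accumulate while patients leave at PD, leaving out time can produce a false association between lower dose and PR that clustering does not remove. The effect of dropping CR cannot be sized.

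It would be wrong to read this as a threat to the trial's main result. The ORR test in Section 5.2.1 uses one best overall response per patient and a Clopper-Pearson interval, and nothing here touches it. The section should be corrected before the exposure-response results are produced or quoted.

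**What to change.** Amend Section 5.5.5 as follows:
- Fit the logistic model with patient as the cluster, by GEE with robust standard errors or with a patient random intercept, and say which.
- Include assessment number as a covariate.
- Pool CR with PR, both in the model and in the dose summary.
- State how the three resulting levels (CR or PR, SD, PD) enter the model: binary with a stated split, cumulative or multinomial. The choice is the sponsor's, but it should be fixed in advance.

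The interval average daily dose can stay as the exposure; no second dose metric is needed to correct the problem described here.

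The cost is a few sentences in the SAP, a little more programming, and possibly wider intervals. Sample size, data collection and the primary and secondary analyses do not change.

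### SAP Section 5.5.5 counts up to 14 untreated days in the first scan interval, so the first average daily dose is understated by 0 to 33% at nominal scan timing

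*SAP*

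**What the plan says.** Section 5.5.5 (Exploratory Analysis) plans a logistic regression of tumor response (PR, SD and PD only) on treatment exposure. It assumes that response at a time point "depends on average daily dose between last and current tumor assessment time points". Its formula for that dose reads: "average daily dose from last tumor assessment to current tumor assessment will be calculated as total dose in the period divided by total days". The same dose variable is summarized descriptively by response category. No separate rule is given for a patient's first interval.

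Section 2.3 treats baseline as a tumor assessment and fixes its window: "The baseline tumor assessment must be performed within 2 weeks prior to, or on" Cycle 1, Day 1. The first follow-up scan is at about 4 weeks, nominally Cycle 2 Day 1. Section 2.1 states "Each treatment cycle is 28 calendar days in duration" and "Poziotinib will be taken orally, once daily (QD) with food".

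Section 6.1 gives the planned daily dose through its relative dose intensity formula (28 × 16 per cycle) and lists reductions to 14, 12, 10 and 8 mg. Both treatment duration and dose intensity in that section are counted from first dose.

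**The concern.** For the first on-treatment scan, the previous assessment can only be the baseline scan. If that scan precedes first dose, the undosed days enter the denominator and add nothing to the numerator. The result then depends on when the baseline scan was booked as well as on what the patient took.

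The error is one-sided and confined to the first interval. Low recorded dose is therefore tied to the week-4 scan, when some eventual responders may not yet have reached PR. This is the only analysis in the SAP that relates administered dose to tumor response. A distortion here could be read as evidence that a higher dose gives more response when dosing never differed.

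**Working it through.** The SAP states no numerical result for this analysis, so there is no figure to reproduce. The check applies its formula to its own schedule.

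**Inputs**
- Planned daily dose 16 mg (Section 6.1), taken once daily (Section 2.1).
- G = days from baseline scan to first dose, 0 to 14 (Section 2.3).
- D = days from first dose to first on-treatment scan: 28 at nominal timing. Section 2.3 allows 21 to 35 under the original protocol (± 7 days) and 28 to 34 under Amendments 1 and 2 (Cycle 2 Day 1 to Day 7).

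**Formula as written, for a patient who misses no dose:** recorded dose = 16 × D / (D + G).

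| D | G | Total dose / total days | Recorded mg/day | Understatement |
|---|---|---|---|---|
| 28 | 0 | 448 / 28 | 16.0 | 0% |
| 28 | 7 | 448 / 35 | 12.8 | 20% |
| 28 | 14 | 448 / 42 | 10.67 | 33% |
| 21 | 14 | 336 / 35 | 9.6 | 40% |
| 34 | 14 | 544 / 48 | 11.33 | 29% |
| 35 | 14 | 560 / 49 | 11.43 | 29% |

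Later intervals run from one on-treatment scan to the next, so full dosing gives 16.0. In the extreme nominal case, a patient with no reduction falls between the 10 mg and 12 mg levels of Section 6.1.

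**How this can reach the regression.** The following is an illustration on assumed inputs. Take 100 patients, all on constant 16 mg, all with G = 7, each with one week-4 scan and one later scan, and model PR against not PR. Recorded dose is 12.8 at week 4 and 16.0 later. Assume 30 responders, of whom 60% (18) are at PR by week 4.
- Mean recorded dose, PR records: (18 × 12.8 + 30 × 16) / 48 = 14.80.
- Mean recorded dose, other records: (82 × 12.8 + 70 × 16) / 152 = 14.27.
- Odds ratio, later against week 4: (30/70) / (18/82) = 1.95. Over a recorded difference of 3.2 mg this is 1.95^(1/3.2) = 1.23 per mg, although the true dose never varied.

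If instead all 30 responders are at PR by week 4 and everyone has both scans, the mean is 14.40 in both groups and the odds ratio is 1. If all 30 respond by week 4 but half of the 70 non-responders leave before the later scan, the means are 14.40 against (70 × 12.8 + 35 × 16) / 105 = 13.87. The odds ratio is then (30/35) / (30/70) = 2.0, or 1.24 per mg.

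**After the fix:** with the first interval starting at first dose, recorded dose is 448 / 28 = 16.0 for every G, and the spurious contrast disappears in all three cases.

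**The case against.** The strongest reply is that this is missing detail more than error. Section 5.5.5 does not say in terms that baseline is the previous assessment for the first scan. A programmer thinking about treatment exposure might start at first dose, or leave the first interval out. That is possible, but the SAP states neither option, baseline is the only earlier assessment it names, and the formula followed literally gives the wrong value.

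Several stronger readings are tempting, and the document does not support them:
- *That fully dosed patients are generally recorded at about 10.7 mg/day.* That needs a 14-day gap with the scan on Cycle 2 Day 1. A baseline scan on Day 1 gives no error, and the SAP does not give the distribution of scan dates.
- *That older Screening images stretch the gap to 30 days.* Section 2.3 says that, when baseline images are incomplete, "the most recently available images of the missing body sites prior to baseline (ie. at Screening) may be sent to Bioclinica". These supplement a baseline assessment that must still fall within its 2-week window, and nothing says they move its date.
- *That every patient contributes a distorted first interval.* Only patients with PR, SD or PD at the first scan do. Those with CR, NE or no post-baseline scan do not.
- *That a false dose-response relation must follow.* The illustration shows none when all responses appear by week 4 and nobody leaves. Real reductions can also offset the artefact: if the later true average were 12.8, recorded dose in the illustration would be equal in both intervals. The dose variable would still be wrong, but no positive relation would show.

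It is also fair that the analysis is labelled exploratory and carries no threshold or decision.

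**Conclusion.** The point holds in limited form. The stated formula lets 0 to 14 undosed days into the first interval and understates a fully dosed patient's first average daily dose by 0 to 33% at nominal timing (16.0 down to 10.7 mg/day). Under the original protocol's earliest permitted first scan, the extreme is 40% (9.6 mg/day). This rests on baseline being the previous assessment for the first scan.

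Because only the first interval is affected, recorded dose is partly confounded with time on treatment. Where some responses first appear after week 4, or non-responders leave early, this can bias both the regression and the dose summaries towards an apparent dose-response relation. The size of that bias depends on response timing, dropout and actual reductions, which the SAP does not give. The odds ratios shown above are illustrations only.

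The primary ORR, DCR, DoR, PFS and the safety analyses do not use this variable. It should be corrected before the analysis is run, but it does not threaten the trial's main conclusions.

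**What to change.** In Section 5.5.5, define each interval as starting at the later of the previous tumor assessment and the date of first dose, and ending the day before the current assessment. Count total dose and total days over exactly that period. State that the same definition applies to the descriptive summaries by PR, SD and PD. This matches the first-dose anchor already used in Section 6.1.

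The cost is one sentence in the SAP and one line of programming. No new data are needed.
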